15.2.2 Secondary Outcome

- (1) To compare the cost-effectiveness of 1HP and 3HP using a societal approach, modeling the incremental cost-effectiveness of 1HP vs 3HP, 6H, and no treatment. This will operate under a separate sub-study protocol.
- (2) Analyze, in each of the health units in the study, the time needed to provide comprehensive care to patients.

15.3 Study Hypotheses

(1) Successful completion of TBT with \geq 90% adherence documented by self-report, pill count, and pharmacologic monitoring.

Hypothesis: Successful treatment with 1HP will be superior to 3HP, with 90% of individuals randomized to 1HP taking >90% of prescribed doses vs 80% of those on 3HP.

(2) Safety of treatment regimens, defined as occurrence of Grade 2 or higher targeted safety events and discontinuation of study medications because of side effects. Targeted safety events are hypersensitivity syndrome, rash, peripheral neuropathy, hepatotoxicity, nausea and vomiting, and drug-related fever.

Hypothesis: We hypothesize that the safety of 1HP will be superior to 3HP, with a rate of targeted adverse events or medication discontinuation of 6% vs. 13% for 3HP.

15.4 Sample Size Considerations

The sample size target is 500 evaluable adolescents and adults. Having each participant complete all of the scheduled drug sampling evaluations will provide approximately 1000 rifapentine and isoniazid pharmacological data points.

Assumptions, Outcome 1:

Successful treatment with 3HP = 80%

In clinical trials, reported completion rates of 3HP have ranged from 84-92% with directly observed therapy. In the CDC-sponsored iAdhere Trial, completion of self-administered 3HP was only 74-76%. In this study, which will use self-administered treatment, we estimate a completion rate of 80%. (Belknap 2017)

Successful treatment with 1HP = 90%

Completion of self-administered 1HP was 97% in the BRIEF TB Study, which was undertaken at research clinics in the ACTG and IMPAACT networks. We estimate that in a more real-world setting adherence will be slightly lower, but should still be at least 90%. We believe that demonstrating \geq 90% completion for 1HP, significantly greater than with 3HP, will provide compelling evidence for clinical practice and treatment guidelines to change.

Based on these assumptions, with an average cluster (household contacts of the index case) size of nearly 2, and an outcome coefficient of variation (CV) of 0.15, near the mean bound using the maximum entropy distribution (Chatfield 2020), a sample size of 250 individuals per arm, 500 total, would provide 80% power for detecting a significant difference at a two-sided 0.05 significance level. The sample size is not inflated for losses to follow up, as those who fail to complete the protocol will have reached a study endpoint.

Assumptions, Outcome 2:

Proportion of participants experiencing Grade 2 or higher targeted safety events with 3HP = 13%.

In TBTC Study 26 and the iAdhere Study, rates of drug-related adverse events with 3HP were 7-8%. In clinical cohort studies, rates of discontinuation for adverse events have been higher. An analysis of patients taking 3HP in Taiwan found that treatment discontinuation due to adverse events occurred in 12%. (Chan, ERJ 2018) A study of health care workers in South Korea reported that 19% of those receiving 3HP had hypersensitivity reactions and 15% discontinued 3HP due to drug reactions. (Jo, in press) We conservatively assume the rate will be 13%.

Proportion of participants experiencing Grade 2 or higher targeted safety events with 1HP = 6%.

In the BRIEF TB trial the rate of targeted safety events was 3%. We would want to demonstrate a reduction from 13% to at least as low as 6% in HIV-negative patients. With a CV of 0.1 (again, in reference to the maximum entropy distribution for the corresponding proportions, which are lower here than for the previous outcome), and the sample size of 250 individuals (about 125 households) in each study arm, we will have about 80% power for detecting a significant difference at a two-sided 0.05 significance level. We would also have 80% power to distinguish between risks of 12% and 5% in the two study arms. Although for convenience we have phrased this in terms of an hypothesis test, our goal is to estimate the difference in safety risks. With this sample size, and risks of 13% and 6% with 3HP and 1HP, respectively, the 95% CI for the risk difference will have a half-width of 3 percentage points. Reporting this CI will enable readers to make their own conclusions regarding non-inferiority of 1HP with respect to 3HP, in addition to superiority. (Dunn 2018)

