Isoniazid has been used in the treatment and prevention of tuberculosis for over 50 years, and its adverse event profile is well known. Rash, fever, jaundice, and peripheral neuritis are the most common INH-related adverse reactions. Concurrent administration of pyridoxine (vitamin B6) prevents INH-related peripheral neuropathy as well as nearly all other nervous system disorders attributable to INH administration. In this study, if a participant develops symptoms of peripheral neuropathy, pyridoxine may be administered at a dose of 25 mg with each dose of INH. The dose of pyridoxine may be increased to 50 mg with each dose of INH if symptoms of peripheral neuropathy persist.

RPT, like other rifamycins, causes red-orange discoloration of body fluids. In trials where RPT was combined with INH and other antituberculosis drugs, rates of adverse reactions were similar between rifampin and RPT, with increased liver aminotransferase activity in about 5% of patients (Priftin package insert 2018).

3HP. In TBTC 26, 3HP was also well-tolerated among study participants

compared to 9H. A synopsis of relevant adverse events and their frequencies is listed in Table 2.

Study	Population	Treatment		Adverse Events		Comment
completion						
Schechter	Household contacts in	3HP	93%	3HP	1%	DOPT, Trial
2006	Brazil	2RZ	94%	2RZ	10%	terminated early
Martinson	HIV+ not on ART,	ЗНР	96%	3HP	8.7/100 PY	DOPT, Continuous
2011	South Africa	6H	84%	6Н	15.4/100 PY	INH more toxic
Sterling 2011	Contacts, other high-	ЗНР	82.1%	3HP	8.2%	DOPT, Toxicity
	risk, >2 yo, US, Can- ada, Brazil, Spain	9Н	69.0%	9Н	5.5%	related to study drugs
Belknap 2017	US, S. Africa, Spain	3HP- DOT	87.2%	3HP- DOT	7.1%	SAT=self-
		3HP- SAT	74.0%	3HP- SAT	8.3%	administered, SAT+
		3HP- SAT+	76.4%	3HP- SAT+	7.9%	text messages
Swindells	HIV+, >13 yo, multiple	1HP	97%	1HP	2.0/100 PY	P value for AE rates
2019	countries	9H	90%	9H	4.6/100 PY	is 0.01
Observational Studies						
Chan 2019	Contacts >12 yo	ЗНР	83.9%	3HP	12.0%	DOPT used for 3HP
	Taiwan	9H	78.8%	9H	9.4%	
Jo 2019	Health care workers,	ЗНР	85.0%	3HP	15%	DOPT used for 3HP
	South Korea	3HR	81.7%	3HR	10%	(19% flu-like
						syndrome with 3HP)

Table 2. Drug-related adverse events in trials of RPT/INH for LTBI treatment

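### The 13% safety-event rate for 3HP is called conservative, but in this superiority test a higher control rate raises power, and 13% exceeds every trial percentage cited

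*Protocol*

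**What the plan says.** Protocol section 15.4 (Outcome 2) builds the 3HP rate from three sources, and SAP section 6 repeats the argument.

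- Randomised trials: "In TBTC Study 26 and the iAdhere Study, rates of drug-related adverse events with 3HP were 7-8"%.
- A Taiwan cohort: "treatment discontinuation due to adverse events occurred in 12"%.
- A South Korean study of health care workers: "19% of those receiving 3HP had hypersensitivity reactions and 15% discontinued 3HP due to drug reactions".

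It then concludes: "We conservatively assume the rate will be 13"%.

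The 1HP rate is fixed separately: "Proportion of participants experiencing Grade 2 or higher targeted safety events with 1HP = 6"%, although "In the BRIEF TB trial the rate of targeted safety events was 3"%. With 250 people (about 125 households) per arm, a between-household CV of 0.1 and two-sided 0.05, the plan claims about 80% power for 13% v 6%, 80% power for 12% v 5%, and a 95% CI half-width of 3 points at 13% v 6%. No power is given for a 3HP rate of 7-8%. SAP section 10.3.1 tests both primary outcomes for superiority at p<0.05.

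**The concern.** A planning assumption is conservative if being wrong about it in the likely direction would leave the trial better off than stated. Here 1HP is set on its own at 6% and the aim is to show that it is lower than 3HP. Raising the 3HP rate widens the gap and raises power, so a cautious choice would sit at the low end of the evidence. The choice made sits near the high end. The one alternative shown, 12% v 5%, keeps the gap at 7 points, so a reader cannot see how strongly power depends on the 3HP rate.

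At stake is how a non-significant safety result is read. If the 3HP rate turns out nearer the trials' figures, such a result would be weak evidence against superiority, yet the plan's text suggests a test with about 80% power under a cautious assumption.

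**Working it through.** **Inputs.** n = 250 per arm, 125 households of 2 per arm, CV k = 0.1, two-sided 0.05 (protocol 15.4); 3HP rate p0 = 0.13; 1HP rate p1 = 0.06.

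**1. The plan's own power figure, 13% v 6%.**

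- Pooled z: Φ{[|p0−p1|√n − 1.96√(2p̄(1−p̄))] / √(p0(1−p0)+p1(1−p1))}, with p̄ = 0.095. This is Φ{(1.1068 − 1.96×0.4147)/0.4117} = Φ(0.714) = 76.2%.
- Unpooled z: SE = √[(0.1131+0.0564)/250] = 0.02604, so Φ(0.07/0.02604 − 1.96) = Φ(0.728) = 76.7%.
- Hayes-Bennett cluster formula: variance per household = 0.1131/2 + 0.0564/2 + 0.1²×(0.13²+0.06²) = 0.08496, so Φ{√(125×0.07²/0.08496) − 1.96} = 76.6%.
- Fisher's exact test by enumeration, no clustering: 72.7%. SAP 10.3.1 names this test for use when few failures share a household.

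As a check on method, the cluster formula gives 80.4% for Outcome 1 (80% v 90%, CV 0.15) and 80.7% for 12% v 5%, both matching the plan's 80%. Only the 13% v 6% figure falls short, by 3 to 4 points.

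**2. The stated half-width.** 1.96 × 0.02604 = 5.1 points, not 3. The standard error alone is 2.6 points.

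**3. Where 13% sits among the cited 3HP rates.** The protocol's table ("Table 2. Drug-related adverse events in trials of RPT/INH for LTBI treatment") and section 15.4 give:

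| Source | 3HP rate |
|---|---|
| Randomised, Brazilian household contacts, observed dosing, ended early | 1% |
| Randomised, TBTC Study 26 | 8.2% |
| Randomised, iAdhere (three arms) | 7.1%, 7.9%, 8.3% |
| Cohort, Taiwan | 12% |
| Health care workers, South Korea | 15% stopped; 19% reactions |

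A further randomised trial is reported only per 100 person-years.

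**4. Power (pooled z, no clustering) by 3HP rate, with the CI half-width in points.**

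| 3HP | 1HP 6% | 1HP 3% | 1HP = 6/13 of 3HP |
|---|---|---|---|
| 7% | 7% (4.3) | 54% (3.8) | 48% (3.8) |
| 8% | 14% (4.5) | 69% (4.0) | 54% (4.1) |
| 10% | 38% (4.7) | 89% (4.3) | 64% (4.5) |
| 13% | 76% (5.1) | 99% (4.7) | 76% (5.1) |
| 15% | 91% (5.3) | >99% (4.9) | 83% (5.4) |

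Power rises down every column. Fisher's exact test gives 11% at 8% v 6%, 48% at 8% v 3.7% and 64% at 8% v 3%.

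**The case against.** **The rates are not like for like.** This stands. The note under the protocol's table says that adverse events were reported differently across studies. The cited figures are drug-related events or discontinuations. This trial counts any Grade 2 or higher targeted event and/or discontinuation for side effects, and SAP 10.2.2 also counts anyone without a last visit after 23 weeks. As an illustration, an 8% underlying rate with an assumed 5% loss becomes 0.08 + 0.05×0.92 = 12.6%. So a reader might infer that 13% is shown to be too high; the documents do not support that. They do not make the broader-endpoint argument either. Nor do losses rescue power: 5% loss in both arms turns 13% v 6% into 17.35% v 10.7%, with 57% power.

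**The direction depends on what is held fixed.** True in one case. With the gap held at 7 points, a higher control rate lowers power: 12% v 5% gives 80%, 13% v 6% gives 76%, 15% v 8% gives 69%. But with 7-8% on 3HP that gap would need 0-1% on 1HP, below the 3% cited.

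**The word may mean only that 13% is below the Korean figures.** That is a possible reading, since the sentence follows them directly. Against the trials and the Taiwan cohort it fails.

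**The plan is cautious elsewhere.** Fair: 6% on 1HP is double the cited 3%, and at 3% power is 69% with 3HP at 8% and 89% at 10%.

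**The stated goal is estimation.** Section 15.4 says so, which softens the power argument, but SAP 10.3.1 still specifies a significance test, and the half-width offered for estimation is itself wrong.

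**Conclusion.** The label is wrong, and two figures beside it need correcting. With 1HP at 6%, at 3% or at the 6/13 ratio, 13% favours power relative to the trials' 7-8%. At the plan's own rates, power is about 76-77% (73% by Fisher's exact test) and the half-width about 5 points. At 8% on 3HP, power is 14% to 69%, depending on the 1HP rate. These results assume 250 analysed per arm and negligible household correlation, as a CV of 0.1 implies.

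Two stronger readings should be resisted. One is that the plan presents 80% as a floor when it is really near a ceiling. The plan says only about 80% and calls it no minimum, and 15% v 6% would give 91% and 13% v 3% 99%. The other is that lower event rates would make the confidence interval less informative. The half-width shrinks from 5.1 points at 13% v 6% to 4.1 at 8% v 3.7%, so it is superiority power that suffers, not absolute precision.

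**What to change.** In protocol 15.4 and SAP 6:

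1. Delete *conservatively*. State that 13% is an expected value, based on cohort discontinuation data for a broader composite endpoint, and that it lies above the trials' 7-8%.
2. Restate the figures at 13% v 6% as about 76-77% power (about 73% with Fisher's exact test) and a 95% CI half-width of about 5 points.
3. Add power and half-width at 3HP rates of 7%, 8%, 10% and 13%, with 1HP at 6%, at 3% and at the 6/13 ratio, as in the table above.

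Leave the sample size, endpoint and analysis unchanged, and keep the risk difference with its CI as the main safety statement, as section 15.4 already intends. The cost is a few sentences and a small table, and a less favourable stated power and precision for a primary outcome.

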15.8.3 Analysis Plan

Analyses will be intention-to-treat for both primary outcomes of successful completion and safety. For the successful completion outcome, losses to follow up (at 4 weeks for Arm 1HP and 12 weeks for Arm 3HP) will be considered as unsuccessful; a sensitivity analysis will be conducted among those not lost in both arms as of 12 weeks. For the safety outcome as of 24 weeks, losses will be considered as failures (safety events).

For the primary outcomes, if fewer than 5% of failures occur in households with 2 or more failures, p-values will be calculated using Fisher's exact test, and 95% confidence intervals (CI) for risk differences will be calculated using the standard asymptotic formula.

Otherwise, within-household correlation will be accounted for using

generalized estimating equations with logit link (for p-value) or identity link (for risk difference CI) and exchangeable correlation structure. If there are convergence problems, a log link function will be used, with delta-method-constructed confidence intervals.

Incidence of active tuberculosis will only be assessed during six months following enrollment but will be evaluated as an exploratory outcome. Incidence will be compared using Kaplan-Meier estimates at 24 weeks and Greenwood's variance formula. This will be a sufficiently rare event that within-household correlation will be ignorable. Censoring will be at last study visit or death. As a sensitivity analysis, TB-free survival will also be analyzed.

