In the BRIEF TB trial the rate of targeted safety events was 3%. We would want to demonstrate a reduction from 13% to at least as low as 6% in HIV-negative patients. With a CV of 0.1 (again, in reference to the maximum entropy distribution for the corresponding proportions, which are lower here than for the previous outcome), and the sample size of 250 individuals (about 125 households) in each study arm, we will have about 80% power for detecting a significant difference at a two-sided 0.05 significance level. We would also have 80% power to distinguish between risks of 12% and 5% in the two study arms. Although for convenience we have phrased this in terms of an hypothesis test, our goal is to estimate the difference in safety risks. With this sample size, and risks of 13% and 6% with 3HP and 1HP, respectively, the 95% CI for the risk difference will have a half-width of 3 percentage points. Reporting this CI will enable readers to make their own conclusions regarding non-inferiority of 1HP with respect to 3HP, in addition to superiority. (Dunn 2018)

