10.3.1 Treatment Success and Safety

A superiority framework will be used for these analyses, with statistical significance defined as p<0.05 for each of the two primary outcomes. No multiplicity correction will be employed.

For each of the primary outcomes, if fewer than 5% of failures (unsuccessful treatment; specified Grade 2 event) occur in households with 2 or more failures, p-values will be calculated using Fisher's exact test, and 95% confidence intervals (CI) for risk differences will be calculated using the standard asymptotic formula.

Otherwise, within-household correlation will be accounted for using generalized estimating equations with logit link (for p-value) or identity link (for risk difference CI) and exchangeable correlation structure. If there are convergence problems with the risk difference estimation, a log link function will be used, with delta-method-constructed confidence intervals for risk differences.

Subgroup analyses will be performed by:

Site Sex Age (dichotomized at overall median) Weight (dichotomized at overall median)

Interaction tests will assess differential effects.

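### Primary safety outcome: the stated 95% CI half-width of 3 percentage points should be about 5 points on the plan's own inputs.

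*Protocol*

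**What the plan says.** Protocol 15.4 (Outcome 2) and SAP 6 carry the same paragraph on the primary safety outcome. It assumes "risks of 13% and 6% with 3HP and 1HP, respectively" and "the sample size of 250 individuals (about 125 households) in each study arm", with a between-household CV of 0.1. It then makes three numerical claims:

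- At 13% versus 6%: "we will have about 80% power for detecting a significant difference at a two-sided 0.05 significance level".
- At a second pair of risks: "We would also have 80% power to distinguish between risks of 12% and 5% in the two study arms".
- On precision at 13% versus 6%: "the 95% CI for the risk difference will have a half-width of 3 percentage points".

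The paragraph puts the weight on the third claim. It says that "our goal is to estimate the difference in safety risks" and that the test is only a convenient way to phrase the calculation. It adds that the reported interval will let readers judge non-inferiority as well as superiority.

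The interval method is given in Protocol 15.8.3 and SAP 10.3.1. It depends on a condition: "if fewer than 5% of failures occur in households with 2 or more failures", Fisher's exact test supplies the p-value and "95% confidence intervals (CI) for risk differences will be calculated using the standard asymptotic formula". Otherwise the plan uses generalized estimating equations (GEE) with an exchangeable correlation, and an identity link for the risk difference.

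**The concern.** A half-width of 3 points looks too small for two arms of 250 with risks near 10%. It also does not fit the power in the same paragraph, since both figures depend on the same standard error. If a 7-point difference is detected with only about 80% power, the interval around it must be much wider than 3 points either side.

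Safety in HIV-uninfected people is the main question the protocol's rationale leaves open for 1HP, and this is one of two primary outcomes. The plan sets no non-inferiority margin for safety. The expected interval width is therefore the main guide a monitoring board, ethics committee or reader has to how much the safety comparison can show. Overstating precision by about 2 points on each side makes the design look more informative than 500 participants allow.

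**Working it through.** **Inputs.** All come from Protocol 15.4 and SAP 6, except the cluster size limit (Protocol 15.5, SAP 5).

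- Risks: p1 = 0.13 (3HP) and p2 = 0.06 (1HP), a difference of 0.07.
- n = 250 per arm, in about 125 households of at most 2.
- CV = 0.1; 95% two-sided, so z = 1.96.

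**Half-width by the standard asymptotic formula.**

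- SE = √[p1(1 − p1)/n + p2(1 − p2)/n] = √[(0.1131 + 0.0564)/250] = 0.02604.
- Half-width = 1.96 × 0.02604 = 0.0510, or 5.10 points.
- Expected interval = 0.07 ± 0.051, or 1.9 to 12.1 points.

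**With the plan's clustering allowance.** The intra-household correlation implied by the CV is ρ = CV²·p/(1 − p), which is 0.0015 at 13% and 0.0006 at 6%. With households of 2, each variance is multiplied by 1 + ρ. The half-width becomes 5.11 points. Assumed correlations of 0.05, 0.1 and 0.2 would give 5.2, 5.4 and 5.6.

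**Attempts to reproduce 3 points.** None succeeds.

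| Calculation | Result (points) |
|---|---|
| Pooled variance, 95% | 5.14 |
| Newcombe interval, 95% | about 5.2 |
| 90% interval | 4.3 |
| 80% interval | 3.3 |
| One standard error | 2.6 |
| 95%, 500 per arm | 3.6 |
| 95%, single arm at 6%, n = 250 | 2.9 |

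The last row is closest, but it is not an interval for a difference. At 250 per arm, ±3 points has confidence level 2Φ(0.03/0.02604) − 1 = 75%. The sample size for ±3 points at 95% is 1.96² × 0.1695/0.03² = 723.5, or 724 per arm.

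**Consistency with the stated power.**

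- A 3-point half-width means SE = 0.03/1.96 = 0.0153. Then 0.07/0.0153 = 4.57, and power = Φ(4.57 − 1.96) = 99.6%.
- Conversely, 80% power at 7 points implies a half-width of 1.96 × 0.07/(1.96 + 0.8416) = 4.90 points.

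The two claims cannot both be true, and the power claim is the one close to correct.

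**Secondary check: the power figures.** No method is named. The Hayes-Bennett formula with c = 125 households per arm and m = 2 is

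power = Φ{√[(c − 1)(p1 − p2)²/v] − 1.96}, where v = p1(1 − p1)/m + p2(1 − p2)/m + CV²(p1² + p2²).

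| Comparison | CV | Plan | Formula |
|---|---|---|---|
| Outcome 1, 90% vs 80% | 0.15 | 80% | 80.1% |
| Safety, 12% vs 5% | 0.1 | 80% | 80.4% |
| Safety, 13% vs 6% | 0.1 | about 80% | 76.2% |

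For the last row, v = 0.0850 and Φ(2.674 − 1.96) = 76.2%. The unpooled normal approximation without clustering gives 76.7%. Fisher's exact test, enumerated with independent participants, gives 72.7% at 13% versus 6% and 77.4% at 12% versus 5%.

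**The case against.** The half-width cannot be defended. The serious objections concern the power point and how much any of this matters.

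**Power.** The plan hedges its figure at 13% versus 6%, names no method, and takes its CV from a cited source. Common methods fall about 3 to 4 points short, which could pass as loose rounding. That is fair as to weight, so this stays a secondary point. Still, one formula reproduces the other two power figures to within half a point and misses only this one.

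**Fisher's test and the asymptotic interval.** These apply only on one branch of the plan's rule. In 200,000 simulated trials with 125 households of two per arm and independent participants, an average of 10.6% of failures fell in households with two failures. The under-5% condition was met in only about 23% of trials. GEE is therefore the likelier analysis, and the Fisher power figures should not replace the plan's text. This does not rescue 3 points, since GEE should give about 5.1 points or more.

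**Impact.** No decision rule uses the 3-point figure, the sample size rests on power, and readers will see the interval actually observed. All of that stands and limits the harm to the planning statement. However, that statement describes the precision of a primary estimate that the plan itself calls the goal.

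**Conclusion.** The stated half-width is wrong in both documents. At risks of 13% and 6% with 250 per arm it is 5.1 percentage points, so the plan's figure is about 41% too small (1 − 3/5.10). This rests only on the plan's own inputs and holds with or without its clustering allowance.

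It could be wider in practice. Losses count as safety events (Protocol 15.8.3, SAP 10.2.2). If the 13% and 6% exclude losses, an assumed 5% or 10% loss in each arm would raise the risks to 17.4% and 10.7%, or to 21.7% and 15.4%. The half-width would then be 6.1 or 6.8 points.

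The power of about 80% at 13% versus 6% is mildly optimistic: about 76-77% by normal-approximation or cluster formula. The 80% at 12% versus 5% is sound by the same methods.

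**What to change.** - **Main change.** In Protocol 15.4 and SAP 6, replace the 3-point half-width with about 5 percentage points at risks of 13% and 6% (5.1 with the plan's CV of 0.1 and households of two).
- **Secondary change.** In the same paragraph, give the power at 13% versus 6% as about 76-77%, keep 80% for 12% versus 5%, and name the method used for both.

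The cost is a wording change in two places. The stated precision, and slightly the power, become less favourable. No extra participants, visits or time are needed, and the analysis is unchanged.
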